1.2 Trial Status and Information That Informed the Updated SAP

1.2.1 Trial Status

The protocol underwent a number of minor changes throughout the study. Two key changes to the protocol are described below.

When the trial opened, participants were required to be scheduled for or have an order for first-time low dose CT for lung cancer screening. Due to fewer people undergoing lung cancer screening (both within the health systems studied in this trial and nationwide), we expanded the inclusion criteria. Eligibility was first expanded in January 2017 at the University of Minnesota and Minneapolis VA to include patients receiving repeat low dose CT for lung cancer screening, in addition to patients receiving first time scans. To further increase enrollment, we added a new site, Allina Health, in June 2018. In September 2018, criteria at the University of Minnesota (UMN) site were expanded to include all people who smoke who were eligible for lung cancer screening on the basis of their age and smoking history. Similarly, the criteria were expanded at the Minneapolis VA to include those who were eligible for lung cancer screening and a part of the lung cancer screening program regardless of their intention to receive another lung cancer screening.

Due to the COVID-19 pandemic-related safety protocols, saliva was no longer collected from participants after March 23, 2020. Thus, cotinine verification of smoking cessation was not able to be assessed after this date. From March 23, 2020 until May 19, 2020,

no participants were sent any biochemical verification. Beginning on May 19, 2020, participants were sent an iCO smokerlyzer to verify abstinence. Additionally, we attempted to send the iCO smokerlyzer to participants to whom we could not send a saliva kit from March 23, 2020 until May 19, 2020 even if those the data collection for those participants was out of window. We paused sending iCO smokerlyzers from July 2020 to December 2020 due to limited product availability.

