1.2.2 Enrolment Summary

The first participant was enrolled on November 11, 2016; the last participant was enrolled on September 25, 2019. A total of 691 participants were enrolled across the three sites. Thirty-one participants withdrew prior to the baseline visits, and an additional 17 participants did not complete the outreach call after the baseline visit; thus, 643 participants were randomized to 4- or 8-week assessment of first stage TLC. A total of 510 participants were incomplete responders and were randomized to TLC vs. TLC + MTM; 126 participants were complete responders and randomized to TLC-Q vs. TLC-M. Seven participants were not randomized a second time. Thus, a total of 636 participants were randomized twice.

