3. Methods to handle missing data: The SAP in the protocol paper specifies that “We will address missing response data using multiple imputation and additional sensitivity analyses.” Multiple imputation will be done using the full conditional specification with predictive mean matching.^{3 4 5} Covariates included in the imputation include age, gender, cigarettes per day at baseline, time to first cigarette at baseline, site, randomized treatment groups, and seven-day point prevalence at 4, 8, and 12 weeks, 6 months, and 12 months, in addition to 18 month long-term cessation. Note that some of these covariates may be missing as well and the full conditional specification enables one to impute these covariates as well. The imputation models for binary and continuous covariates will use logistic and linear regression models with main effect terms for all the other covariates. Twenty complete datasets will be imputed and the estimates from each the analysis of each complete datasets will combined using Rubin’s combining rules. Participants who died will be recorded as a “failure,” and we will not stochastically impute their endpoint. As a sensitivity analysis, we will also stochastically impute a cessation endpoint for those who died during the study. Note that only the primary endpoint will be imputed, imputation for other secondary endpoints will not be considered. Sensitivity analysis includes assuming those without data are still smoking and complete case analysis. Additional sensitivity analyses which may be considered (which do not assume that the missigness is ignorable) include joint models for longitudinal smoking cessation and nonresponse, pattern mixture models, and selection models.

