4. Lung Cancer Screening Results: Secondary aim 4 addresses whether or not lung cancer screening results moderate smoking cessation outcomes. Due to changes in the eligibility criteria, participants may or may not have undergone lung cancer screening at any time during the 1 year of treatment provided by the study. For the purposes of this analysis, we will use the Lung RADS score from the first *screening* CT during the treatment period or just prior to the outreach call (the electronic medical record is queried up to 6 months prior to enrolment). When the Lung RADS score is considered an ordinal measure, those without CT scans will be considered to have a Lung RADS score of 0. As a sensitivity analysis, we will also group those participants with Lung RADS score of 1.

¹ Fu SS, Rothman AJ, Vock DM, et al. Program for lung cancer screening and tobacco cessation: Study protocol of a sequential, multiple assignment, randomized trial. *Contemp Clin Trials*. 2017;60:86-95. doi:10.1016/j.cct.2017.07.002

² FDA (2019). Adjusting for Covariates in Randomized Clinical Trials for Drugs and Biologics with Continuous Outcomes. *Draft Guidance for Industry*.

³ Liu Y, De A. Multiple Imputation by Fully Conditional Specification for Dealing with Missing Data in a Large Epidemiologic Study. *Int J Stat Med Res*. 2015;4(3):287-295. doi:10.6000/1929-6029.2015.04.03.7

⁴ Van Buuren, S. (2007). "Multiple Imputation of Discrete and Continuous Data by Fully Conditional Specification." *Statistical Methods in Medical Research* 16:219–242.

⁵ Van Buuren, S. (2012). *Flexible Imputation of Missing Data*. Boca Raton, FL: Chapman & Hall/CRC.

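### The aim 4 moderator can be measured after second-stage randomization, and the SAP has no rule or sensitivity analysis on scan timing

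*SAP*

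**What the plan says.** SAP section 1.3, item 4, states the aim: "Secondary aim 4 addresses whether or not lung cancer screening results moderate smoking cessation outcomes". Because eligibility was widened, it notes that "participants may or may not have undergone lung cancer screening at any time during the 1 year of treatment provided by the study". The moderator is the Lung RADS score from the first screening "CT during the treatment period or just prior to the outreach call", and "the electronic medical record is queried up to 6 months prior to enrolment". On the ordinal scale, "those without CT scans will be considered to have a Lung RADS score of 0". The one sensitivity analysis in item 4 moves the no-scan participants into the group with score 1.

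Section 1.2.2 gives the timing of the design: "643 participants were randomized to 4- or 8-week assessment of first stage TLC". Participants were then re-randomized according to response. Section 1.2.1 explains why a scan is no longer an entry condition for everyone. From September 2018 the University of Minnesota site could enrol on age and smoking history alone, and the VA site could enrol those who were "a part of the lung cancer screening program regardless of their intention to receive another lung cancer screening".

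**The concern.** A treatment-by-moderator comparison inherits the protection of randomization only if the moderator is fixed before the assignment being compared. Item 4 puts three kinds of scan into one variable: those before treatment, those between the two randomizations, and those after the second. It adds a no-scan level that can only be known when the window closes. Scan dates are not used to restrict, stratify or test the analysis.

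If being scanned during the year depends on the assigned contact schedule, or on having quit, then the level a participant occupies is partly a consequence of treatment. An apparent difference in treatment effect between levels could then arise with no true moderation, and a true difference could be distorted. At stake is whether aim 4 can support a statement about who benefits from second-stage treatment. The primary comparison is not touched.

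**Working it through.** The SAP gives no figure for aim 4, no count of participants with a CT and no distribution of CT dates, so there is no stated result to reproduce. Three things can be checked.

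**Inputs.** Item 4: look-back of 6 months (about 26 weeks) and a treatment period of 1 year (52 weeks). Section 1.2.2: assessment at r = 4 or 8 weeks. Item 1 of section 1.3: outcome at 78 weeks, covering the past 7 days and past 6 months. Assumptions: the treatment year starts at the outreach call, and second-stage randomization follows the assessment directly.

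**1. Can the moderator be set after randomization?** Yes. The window stays open for 52 − 4 = 48 or 52 − 8 = 44 weeks after second-stage randomization. That is 48/52 = 92% or 44/52 = 85% of the treatment year, and 48/78 = 62% or 44/78 = 56% of the full 26 + 52 week window. These are shares of calendar time, not of scans. The value 0 is settled only at the end of the window, so for the no-scan group it always comes after randomization.

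**2. What share of scans falls after it?** Let q be the share of first scans made before the outreach call, with the rest spread evenly over the year. The share after second-stage randomization is (1 − q)(52 − r)/52.

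| q (assumed) | r = 4 | r = 8 |
|---|---|---|
| 0 | 92% | 85% |
| 0.25 | 69% | 63% |
| 0.50 | 46% | 42% |
| 0.75 | 23% | 21% |
| 0.90 | 9% | 8% |

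It drops below half once q exceeds 1 − 0.5 × 52/(52 − r), which is 46% (r = 4) or 41% (r = 8). With q = 0 but early clustering (exponential waiting time of mean m weeks, truncated at 52), the share is (e^(−r/m) − e^(−52/m))/(1 − e^(−52/m)). For m = 4, 8, 13 and 26 this gives 37%, 61%, 73% and 84% (r = 4), and 14%, 37%, 53% and 69% (r = 8). The documents do not say which of these applies.

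**3. What would dependence do?** Assume abstinence of 12% with TLC and 22% with TLC+MTM, a 10-point effect in everyone and no true moderation. Let p be abstinence in an arm, and let u1 and u0 be scan uptake in quitters and non-quitters. Then P(abstinent | scanned) = p·u1/(p·u1 + (1 − p)·u0), and for the unscanned u is replaced by 1 − u. Take u0 = 40% throughout.

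- *Uptake 40% for all:* 10 points in both groups; false contrast zero.
- *Quitters 50% in both arms:* scanned 26.1% vs 14.6% (11.5 points), unscanned 19.0% vs 10.2% (8.8 points). The odds ratio is about 2.07 in the scanned, in the unscanned and overall (22% vs 12%), so a logistic interaction would be zero.
- *Quitters 50% in TLC+MTM only:* scanned 0.110/(0.110 + 0.312) = 26.1%, unscanned 0.110/(0.110 + 0.468) = 19.0%, against 12% with TLC. Differences are 14.1 and 7.0 points.
- *Quitters 55% in TLC+MTM only:* scanned 0.121/(0.121 + 0.312) = 27.9%, unscanned 0.099/(0.099 + 0.468) = 17.5%. Differences are 15.9 and 5.5 points.

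The last two cases show a false contrast of about 7 and 10 points. In all four, uptake does not depend on the CT result, so among scanned participants the effect is the same at every score. The false contrast lies wholly between the scanned and the no-scan level coded 0.

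**The case against.** Several stronger readings are tempting, and the document does not support them.

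- *Most scans come after second-stage randomization.* The 92% and 85% need an even spread over the year and leave out scans before the outreach call, which the definition includes. The first scan in the window is used. Participants initially had a scan scheduled or ordered at entry, and criteria without a planned scan came only in September 2018, with enrolment closing in September 2019. Early clustering is plausible.
- *A late result cannot affect the outcome.* The outcome looks back 6 months from week 78, so it covers about weeks 52 to 78. A scan within the treatment year precedes it. The fault is measurement after randomization, not a result that arrives too late to act.
- *The bias is 7 to 10 points.* That needs higher uptake among quitters in one arm only, for which the SAP gives no basis.
- *Deaths and withdrawals drive it.* Table 1 shows 6 deaths and 15 withdrawals at Week 52, which is 21/636 = 3.3%. Nothing says that withdrawal ends the record query.
- *The 6-month look-back is an error.* A repeat screener last scanned earlier may already know a result that is not counted, but the number is unknown and the limit is a defined choice.

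It can also be said that the aim 4 model may be in the protocol paper, and that item 4 speaks of moderating cessation outcomes without naming a treatment interaction. That stands, and it is why the conclusion is conditional on such an interaction. It does not remove the point, because item 4 itself fixes how the moderator is defined and does so without regard to timing.

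**Conclusion.** The concern holds in a limited form. By the SAP's own windows, the aim 4 moderator may be determined after second-stage randomization for an unstated share of participants, and this always applies to the no-scan value. No rule or sensitivity analysis deals with it. Any treatment-by-result interaction that includes those participants is not protected by randomization.

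No size can be given. The bias is zero if scan uptake depends on neither arm nor quitting. On the odds-ratio scale it is also zero in the illustration where uptake depends on quitting equally in both arms. Where it arises, it does so mainly through the contrast with the group coded 0. The conclusion assumes that second-stage randomization takes place at about 4 or 8 weeks and that aim 4 is meant to say something about treatment effects. It concerns a secondary aim only.

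**What to change.** In item 4 of section 1.3:

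1. Classify each CT by date as before the outreach call, between the two randomizations, or after the second. Report the counts, with the number without a scan, by randomized group.
2. Add a moderation analysis in which only scans dated before the relevant randomization define the moderator, and base any claim of treatment-effect moderation on it.
3. Keep the analysis using all scans in the treatment year, labelled as descriptive association.

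This needs the scan dates from the same medical record and a few lines of SAP text. The downside is that fewer participants have a result in the moderation analysis. Scans ordered at entry but done after week 4 or 8 drop out of it for second-stage comparisons, so the aim 4 interval will be wider. Keeping the all-scan analysis preserves that information. A longer look-back is optional and a matter of judgement. The primary analysis does not change.

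### In the ordinal Lung-RADS analysis for secondary aim 4, people with no CT are placed on the result scale (score 0, or with score 1), so a trend mixes having been scanned with the screening result

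*SAP*

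**What the plan says.** Section 1.3, item 4, states the question: "Secondary aim 4 addresses whether or not lung cancer screening results moderate smoking cessation outcomes". It then explains that, because eligibility was widened, "participants may or may not have undergone lung cancer screening at any time during the 1 year of treatment provided by the study". Section 1.2.1 gives the background: from September 2018 the University of Minnesota site was opened to "include all people who smoke who were eligible for lung cancer screening on the basis of their age and smoking history", and the Minneapolis VA criteria no longer depended on an intention to be screened again.

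The score is taken from the first screening "CT during the treatment period or just prior to the outreach call". The coding rule follows: "When the Lung RADS score is considered an ordinal measure", "those without CT scans will be considered to have a Lung RADS score of 0". The alternative is: "As a sensitivity analysis, we will also group those participants with Lung RADS score of 1".

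The SAP states no separate no-CT category or indicator and no analysis limited to scanned participants. It does not give the number unscanned or the form of the aim 4 model; item 2 of the same section extends the adjusted models to secondary aims 2 and 3 only.

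**The concern.** Lung-RADS can order people who have a result. Someone without a CT has none, so code 0 asserts an ordering, one step below score 1, that no observation supports. A trend over the scale 0 to 4 then combines two contrasts: scanned against unscanned, and the gradient among actual results. Only the second answers aim 4.

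Scan status is unlikely to be arbitrary. By the SAP's own account it is tied to site, enrolment date and, at the VA, intention to be screened. The SAP has no data on whether these relate to quitting, but they plausibly could. If abstinence differs by scan status, the score can show a trend with cessation; if the treatment effect differs by scan status, it can show moderation. Either could appear with no gradient at all among scanned people, and a reader of the report could not tell the difference.

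The sensitivity analysis moves the unscanned by one step but leaves them on the scale. Both codings are biased in the same direction, so agreement between them would reassure without reason.

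**Working it through.** The SAP states no figure for aim 4, so there is none to reproduce. The check has to be an illustration.

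**Inputs from the SAP.** Section 1.2.2: "A total of 510 participants were incomplete responders and were randomized to TLC vs. TLC + MTM". Section 1.2.4: 10–15% long-term abstinence on TLC alone (midpoint 12.5%) and a design difference of 10 percentage points.

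**Assumptions, not in the SAP.** Unscanned share *u* from 10% to 50%; scores 1/2/3/4 at 50/30/10/10% of the scanned; the score entered as a linear term in a logistic model.

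**Step 1: what the scale measures.** Among the scanned, the mean is 0.5×1 + 0.3×2 + 0.1×3 + 0.1×4 = 1.8. The variance is (0.5×1 + 0.3×4 + 0.1×9 + 0.1×16) − 1.8² = 4.2 − 3.24 = 0.96. With the unscanned coded *c*, the share of score variance due to scan status alone is

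u(1−u)(1.8−c)² / [u(1−u)(1.8−c)² + (1−u)×0.96].

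For u = 0.1 and c = 0: 0.09×3.24 = 0.2916; 0.9×0.96 = 0.864; 0.2916/1.1556 = 25%. For u = 0.5 and c = 0: 0.81/(0.81 + 0.48) = 63%. This describes the coding; it is not itself a bias.

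**Step 2: moderation with no gradient by result.** Let abstinence be 12.5% on TLC for everyone. Let MTM raise it to 22.5% in the scanned at every score and leave it at 12.5% in the unscanned. The true treatment-by-score slope among people with a result is 0. The table gives the value to which the fitted slope tends (log-odds per step), and the rejection rate of a two-sided 5% Wald test of that slope (n = 510, 4,000 simulated trials per setting).

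| Unscanned | Variance share, c=0 / c=1 | Slope, c=0 / c=1 | Rejection, c=0 / c=1 | Rejection, no-CT indicator or scanned only |
|---|---|---|---|---|
| 10% | 25% / 6% | 0.082 / 0.046 | 5.0% / 4.2% | 4.3% |
| 20% | 40% / 12% | 0.134 / 0.087 | 10.0% / 6.3% | 4.8% |
| 30% | 50% / 17% | 0.171 / 0.126 | 11.0% / 5.7% | 4.8% |
| 40% | 57% / 21% | 0.199 / 0.162 | 13.8% / 6.6% | 4.8% |
| 50% | 63% / 25% | 0.222 / 0.196 | 17.2% / 8.1% | 4.6% |

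Pooling with score 1 brings the rejection rate close to nominal, but at 50% unscanned the slope itself is nearly as biased as with code 0 (0.196 against 0.222).

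**Step 3: no heterogeneity.** With +10 points in both groups and 20% or 40% unscanned, rejection is 4.9% and 5.3% (c = 0), 4.8% and 4.6% (c = 1), and 4.2% and 4.8% (indicator). The coding alone does not inflate the test.

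**Step 4: another score mix, and association instead of moderation.** With scores at 45/35/12/8% and control abstinence of 15%, the interaction odds ratio per step is 1.09, 1.14, 1.18 and 1.24 (c = 0) and 1.05, 1.10, 1.14 and 1.22 (c = 1) at 10, 20, 30 and 50% unscanned; scanned only, it is 1.00. If the question is instead whether score relates to abstinence, with 15% in the unscanned and 22% in the scanned at every score, the odds ratio per step is 1.07, 1.11, 1.13 and 1.17 (c = 0) and 1.04, 1.07, 1.10 and 1.16 (c = 1), again against a true 1.00.

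**The case against.** The strongest objection is that the SAP does not state the aim 4 model. If the score levels enter as separate categories, code 0 is merely a label for a no-CT group and the objection largely goes away. The conditional wording, "When the Lung RADS score is considered an ordinal measure", also implies a non-ordinal form that may be the main one and may treat the unscanned properly. Both points stand. They are why the concern is limited to the ordinal form with a trend, which is nevertheless the natural use of an ordinal measure.

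Second, the SAP recognised the problem, fixed a code in advance and added a sensitivity analysis; with 10–40% unscanned, pooling gives 4.2–6.6% false positives. That is fair as to the test, but the slope remains biased and nothing in the plan isolates the gradient among results.

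Third, the illustration puts the whole MTM effect in the scanned. With 5 points in the scanned and none in the unscanned, rejection is 5.4, 6.0, 5.4 and 8.1% (code 0) and 5.5, 4.8, 4.4 and 5.0% (pooled) at 10, 20, 30 and 50% unscanned, so inflation is negligible except with code 0 at 50%. This stands: the harm is conditional and usually modest.

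Fourth, the remedy costs precision. It does, but the precision given up came from people who have no result.

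**Conclusion.** The concern holds. The SAP sets an explicit rule that places people without a CT on a scale meant to represent screening results, and its sensitivity analysis keeps them there. If the score is used as a trend, the estimate is not purely a gradient by result.

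The size depends on three things the SAP does not give: the unscanned share, the score mix, and how far abstinence or the treatment effect differs by scan status. Under the stated assumptions, false moderation is found in 5–17% of trials with code 0 and 4–8% with pooling, against 4–5% when the two contrasts are separated. The treatment-by-score slope is not biased if the treatment effect is the same in scanned and unscanned people. The point affects one form of one secondary aim and leaves the primary analysis untouched. It should be changed because the correction is cheap.

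On timing, the CT may fall anywhere in the treatment year, so for some participants the moderator is measured after randomisation. The SAP does not show that treatment alters scan uptake, so this is a caveat and not part of the finding.

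**What to change.** In the ordinal analysis, add an indicator for no screening CT and, in moderation models, its interaction with treatment, so that the Lung-RADS slope is estimated from scanned participants alone. Report the unscanned as their own group, with numbers by arm and site. Replace or supplement the sensitivity analysis that pools them with score 1 by one limited to scanned participants. State the form of the aim 4 model.

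Optionally, keep the CT window as it is, say that CTs after randomisation make the score a post-randomisation moderator, and add a sensitivity analysis limited to participants whose first screening CT precedes second-stage randomisation. That analysis would lose participants, and the SAP does not show how many.

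The cost is SAP wording and one or two model terms; only the optional analysis needs the CT dates. Precision falls: in the illustration the standard deviation of the estimated slope rises from 0.23 to 0.27 at 10% unscanned and from 0.22 to 0.39 at 50%. With few unscanned, the no-CT interaction may not be estimable (8% of simulated trials at 10% unscanned); the scanned-only analysis then serves.
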